4.4.5.2 Secondary Endpoints

4.4.5.2.1 Progression-Free Survival

PFS is defined as the time interval from first treatment to objective tumor progression or death. Accordingly, the precise definition of progression and the timing of CT scans to document progression are very important. Every effort must be made to assure that timeframes for post-treatment CT scans are achieved, so that both treatment groups can be usefully compared.

Assessments must be adequate to evaluate target lesions, non-target lesions, and to search for new lesions.

The secondary endpoint of PFS will be based on the investigator's assessment using RECIST v1.1 response guidelines. PFS will be defined as the time from the day of first treatment to the start of disease progression or death (any cause), whichever occurs first. Subjects who do not have disease progression or have not died will be censored at the date when the last tumor assessment determines a lack of progression. If a subject begins a new anti-cancer therapy or has radiotherapy or surgery at a lesion site prior to documented progression (or death), the subject will be censored at the last assessment where the subject was documented as progression free prior to the intervention.

The Kaplan-Meier curve for PFS and the median PFS will be presented for the FAS.

Additionally, an investigator assessed PFS analysis that includes both investigator-judged PD according to RECIST v1.1 and symptomatic deterioration will be provided.

A binary endpoint for PFS will also be analyzed at milestone time points. The number and percentage of subjects who are progression free based on the above definition at 6, 9, 12, 18, and 24 months will be summarized within the FAS. The two-sided 90% exact binomial confidence interval for the PFS at each time point will be calculated using the Clopper-Pearson method.

A recently published meta-analysis concluded that in checkpoint inhibitor trials 6-month PFS rate is recommended as an endpoint because it is the best predictor of 12-month OS rate. In the absence of prospective validation, the decision adopted is to retain 6-month PFS rate as a secondary endpoint with the aim of complement the primary endpoint ORR in the interpretation of trial results as a whole.

In case some additional immune-related responders are observed, PFS analysis using iRECIST criteria will be performed. The iRECIST modification requires a confirmation of PD at least 4 weeks later with imaging; once confirmed, the date of progression is defined as the first date that the total tumor burden was shown to have increased by at least 20% compared with the nadir. For subjects who are not evaluated by iRECIST criteria, their disease progression based on RECIST v1.1 response guidelines will be used.

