## **9.6 Prior/Concomitant Medications**

All concomitant medications (including Long Term FU anti-cancer treatments) and prior medications will be coded to Anatomic-Therapeutic-Chemical (ATC) drug classes and preferred drug names using the WHO Drug Dictionary. The incidence of prior and concomitant medication usage will be summarized by ATC class and preferred drug names for the FAS.

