4.3.2 Missing or Partial Dates

All data will be listed and summarized as captured in the electronic Case Report Form (eCRF) or transferred from external sources (e.g., lab, ECG). It may be necessary to impute incomplete dates to correctly assign events to a period or to calculate durations.

For prior and concomitant medications, AEs, and cancer history dates the following rules will apply:

Missing	Rule for start date	Rule for end date	Flag for imputation
Day	First of month	Last of month*	D
Month [†]	1 January	31 December*	M
Year [†]	First Treatment Date	Date of Data Cutoff/Lock	Y

* Unless the imputed start date is before first visit date, in which case first visit date is used; or the imputed stop date is after last visit date in which case last visit date available is used.

† It is assumed that a missing Month implies a missing Day as well, and that a missing Year implies a missing Month and Day.

If the imputation of an AE start date leads to a date prior to the date of first vaccination, and it is possible that the AE start date can be on or after date of first vaccination based on partial date information (e.g., occurred on the same month), it will be set to the date of first vaccination to be conservative. In the event the imputation of an end date leads to a date after the death date of a subject, the death date will replace the imputed date.

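### Backward imputation of partial therapy start dates can place next-line drug therapy before the progression that led to it, turning a true PFS event into a censored time

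*SAP*

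**What the plan says.** **Censoring rule.** SAP 4.4.5.2.1 takes a new therapy, or radiotherapy or surgery at a lesion, as the trigger: "If a subject begins a new anti-cancer therapy or has radiotherapy or surgery at a lesion site prior to documented progression (or death". The consequence is that "the subject will be censored at the last assessment where the subject was documented as progression free prior to the intervention". The therapy start date therefore decides between event and censoring. Protocol 9.7.2.1 has the same rule.

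**Imputation rule.** SAP 4.3.2 introduces its table with "For prior and concomitant medications, AEs, and cancer history dates the following rules will apply". For a start date, a missing day becomes "First of month", a missing month becomes 1 January, and a missing year becomes "First Treatment Date". The only floor on a medication start is in the footnote: "Unless the imputed start date is before first visit date, in which case first visit date is used". A further adjustment exists for adverse events alone ("If the imputation of an AE start date leads to a date prior to the date of first vaccination"). Neither refers to progression or to the last dose.

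**Why the second rule reaches the first.** Protocol 9.6 counts next-line drugs as concomitant medications: "All concomitant medications (including Long Term FU anti-cancer treatments) and prior medications will be coded". SAP 4.4.7.7 includes any medication started after the first trial product, and SAP 4.3.1 describes long-term follow-up as collecting concomitant medication and vital status.

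**The concern.** Moving a start date back is cautious for adverse events, because it makes them more likely to count as treatment emergent. For a date that triggers PFS censoring, the same rule can remove events.

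Protocol 4.2.5.1 recommends that further therapy wait until progression is documented, so the usual true order is scan first, therapy second. Imputation can only move the therapy earlier. It can therefore turn an event into a censored time but not the reverse, and it does so only in subjects who progressed and moved on to other treatment. That is informative censoring in the favourable direction for the Kaplan-Meier estimate. PFS is secondary, but the SAP keeps the 6-month PFS rate specifically to help interpret the ORR result.

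**Working it through.** The plan states no figure on this point, so there is none to reproduce.

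**1. One record (assumed dates).** First dose 21 January 2019. Week 10 scan (Day 64) on 25 March, no progression. Week 22 scan (Day 148) on 17 June, progression. Next drug started on 24 June but recorded only as June 2019.
- Imputed start: 1 June, 16 days before the progression scan.
- Result: the event at Day 148 becomes a censored time at Day 64, which is 148 − 64 = 84 days earlier.
- If progression is at Week 10 instead, there is no post-baseline progression-free scan to censor at. The SAP does not say what happens then; Day 1 is the natural reading.

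**2. How often the order reverses.** With the day missing, it reverses when scan and therapy start fall in the same calendar month and the scan is not on the 1st. Taking every scan date in a four-year cycle:

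| Scan-to-therapy gap (assumed) | Day missing | Month missing |
|---|---|---|
| 7 days | 74% | 98% |
| 14 days | 51% | 96% |
| 21 days | 28% | 94% |
| 28 days | 5% | 92% |
| 30 days | 0% | 92% |

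The month-missing column ignores the first-visit floor. With the year missing, the imputed date precedes every post-baseline progression.

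**3. Events lost (assumed rates).** Let 60% of progressors start a new drug, with the gap uniform over 7 to 35 days, and let 10 to 30% of the dates lack the day only. The mean reversal share over those 29 gaps is 0.298. The share of events lost is q = 0.60 × (0.10 to 0.30) × 0.298:
- low: 0.60 × 0.10 × 0.298 = 1.8%
- high: 0.60 × 0.30 × 0.298 = 5.4%

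Even if all 33 or 35 subjects in a cohort progressed, this is about 0.6 to 1.9 subjects (33 × 0.018 to 35 × 0.054). One subject is 3.0% or 2.9% of a full cohort.

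**4. Kaplan-Meier PFS at 6 months.** Assume 55% progress at Week 10 and 25% of those remaining progress at each later scan. Six months is about Day 183, so only the Day 64 and Day 148 scans count.
- True value: 0.45 × 0.75 = 33.75%.
- With the rule, reversed Week 10 progressors leave at Day 1 and reversed Week 22 progressors leave at Day 64: S = [0.45 / (1 − 0.55q)] × [0.75 / (1 − 0.25q)].
- q = 0.018: S = 34.2%, a rise of 0.5 points.
- q = 0.054: S = 35.3%, a rise of 1.5 points.

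**5. Binary 6-month rate.** The SAP plans a count and percentage in the FAS with a Clopper-Pearson interval, and does not say how subjects censored before the milestone are counted.
- If they are not counted as progression free, the lost Week 10 and Week 22 events change nothing, since those subjects were already failures. A reversed Day 190 progression, censored at Day 148, leaves the numerator: the change is −0.3375 × 0.25 × q, or −0.2 to −0.5 points.
- If they are counted as progression free, the rate rises by (1 − 0.3375) × q, or 1.2 to 3.6 points.

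**The case against.** **The link is inferred.** SAP 4.3.2 does not name post-treatment cancer therapies, which have their own section (4.4.7.9). The OS section refers back to the imputation rules and the PFS section does not. Protocol 9.6 is mainly about coding. This has some force, but Protocol 9.6 expressly places follow-up anti-cancer treatments among concomitant medications, SAP 4.4.7.7 agrees, and nothing exempts PFS. A programmer following the text would apply the rule.

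**Other data contradict the imputed order.** Last-dose date and discontinuation reason are collected, and Protocol 8.2.2.2 prohibits other anti-cancer therapy during the trial. An imputed start during trial treatment would look wrong. That is true, but no text lets those data override the imputed date. The objection supports writing the override down.

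**The effect is small.** This stands. A 90% Clopper-Pearson interval for 10 of 33 runs from 17% to 46%, far wider than any shift above.

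**Stronger readings the documents do not support.**
- A reader might infer that radiotherapy and surgery dates are pulled back in the same way. SAP 4.3.2 does not name non-drug therapies (4.4.7.8), so no clear imputation rule covers them. That is a gap, not a wrong rule.
- A reader might infer that the 6-month PFS rate is inflated. That holds for the Kaplan-Meier estimate; the planned rate is binary and could move either way.
- A reader might infer that partial dates will be common because follow-up is by quarterly telephone. The documents give no rate, and the end-of-treatment visit within 28 days of withdrawal overlaps most of the window in which a missing day matters.

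**Conclusion.** The concern holds for subsequent anti-cancer drugs. Followed as written, the two SAP rules can convert a documented progression into a censored time one scan interval earlier, or leave no post-baseline progression-free scan when progression was at Week 10. The Kaplan-Meier PFS curve and median are biased upward; the direction for the binary milestone rates is open and may be slightly downward.

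The reversal shares are calendar arithmetic for the stated gaps. The overall size, about 2 to 5% of events and 0.5 to 1.5 points on 6-month Kaplan-Meier PFS, rests on assumed rates of further therapy, gaps, missing days and progression, none of which the documents give. The ORR decision is unaffected. This is a minor point, worth settling before database lock because each affected record would be wrong.

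**What to change.** Add to SAP 4.3.2 and 4.4.5.2.1, for PFS and duration-of-response derivations:

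1. Impute a partial start date of subsequent anti-cancer drug therapy to the latest date its recorded parts allow, and not before the last dose of trial product where those parts permit.
2. Treat a therapy as preceding progression only if its recorded date parts show that it did.
3. Apply the order rule in item 2 to partially dated lesion radiotherapy or surgery, but without the last-dose floor, since these may occur on treatment.

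The duration-of-response section states no new-therapy censoring at present; naming it keeps the derivations consistent if the same censoring is programmed there.

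The cost is SAP wording, with no new data collection. The downside is that a few therapies truly begun before progression in the same month would be classed as following it, which errs toward counting events.

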### 4.2.3 Long Term Follow-up Period

During the Long-Term follow-up (LTFU) period, subjects will be followed by phone contact at quarterly intervals for survival status assessment and potential autoimmune or immune-mediated clinical manifestations. The FU period may be extended up to 2 years.

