## **9.7.2 Secondary Efficacy Analyses**

### **9.7.2.1 Progression-Free Survival**

PFS is defined as the time interval from first treatment to objective tumor progression or death. Accordingly, the precise definition of progression and the timing of CT scans to document progression are very important. Every effort must be made to assure that timeframes for FU CT scans are achieved. Assessments must be adequate to evaluate target lesions, non-target lesions, and to search for new lesions.

The secondary endpoint of PFS will be based on the investigator's assessment using RECIST 1.1 response guidelines. PFS will be defined as the time from the day of first treatment with trial product to the start of disease progression or death (any cause), whichever occurs first. Subjects who do not have disease progression or have not died will be censored at the date when the last tumor assessment determines a lack of progression. If a subject begins a new anti-cancer therapy or has radiotherapy or surgery at a lesion site prior to documented progression (or death), the subject will be censored at the last assessment where the subject was documented as progression free prior to the intervention.

The Kaplan-Meier curve for PFS and the median PFS will be presented for the FAS Set.

Additionally, an investigator assessed PFS analysis that includes both investigator-judged PD according to RECIST 1.1 and symptomatic deterioration will be provided.

A binary endpoint for PFS will also be analyzed at milestone time points. The number and percentage of subjects who are progression free based on the above definition at 6, 9, 12, 18, and 24 months will be summarized within the FAS. The two-sided 90% exact binomial confidence interval for the PFS at each time point will be calculated using the Clopper-Pearson method.

A recently published meta-analysis concluded that in checkpoint inhibitor trials 6-month PFS rate is recommended as an endpoint because it is the best predictor of 12-month OS rate ([Ritchie et al., 2018](#)). In the absence of prospective validation, the decision adopted is to retain 6-month PFS rate as a secondary endpoint with the aim of complement the primary endpoint ORR in the interpretation of trial results as a whole.

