4.3 Data Handling Conventions

4.3.1 Visit Windowing

For analysis purposes, all by-visit data will be mapped to a visit window to maintain consistency of therapeutic duration among summaries at each time point. The visit that occurs out of window may be analyzed along with data from an earlier or later visit if the trial day falls into a different visit window category. In addition, unscheduled visits that fall into the window for a scheduled visit may be counted along with that visit, such that no data are excluded from potential summaries. In the case of multiple visit results within a visit window, descriptive statistics will be based on non-missing data from a visit closest to the scheduled visit day. Categorical summary will be based on the worst non-missing results. For the current trial, visits will be mapped by trial day as follows:

Table 1 Windowing Schema for Screening and the Treatment Period

Visit Number	Visit	Planned Trial Day	Protocol Allowed Visit Window (days)	Trial Day Window for Analysis (days)
1	Screening	Within 28 days of first treatment	-28 to -1	<1
2	Week 1	1	1	1-11
3	Week 4	22	18-26	12-32
4	Week 7	43	39-47	33-53
5	Week 10	64	60-68	54-74
6	Week 13	85	81-89	75-95
7	Week 16	106	102-110	96-127
8	Week 22	148	144-152	128-169
9	Week 28	190	183-197	170-232
10	Week 40	274	267-281	233-316
11	Week 52	358	351-365	317-396
12	Week 64	442	428-456	397-484
13	Week 76	526	512-540	485-568
14	Week 88	610	596-624	569-652
15	Week 100	694	680-708	> 652

As long-term FU visits only collect concomitant medication and vital status data, no windowing will be needed for this trial phase.

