4.3.3 Data Handling Conventions for Efficacy Analyses

Subjects who have no record of CR/PR and withdraw early from the trial or are lost to follow up will be considered as non-responders for the ORR analyses.

For PFS, if a subject has no date of death and has not progressed by the time of the analysis, the subject will be censored at the last radiologic assessment showing no progression has occurred. For sensitivity analyses on the FAS, if a subject has no post-baseline radiologic assessment, they will be censored on Day 1.

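### Landmark PFS is planned as a simple proportion on a censored endpoint, with no scoring rule for censored subjects and landmarks (6, 9 and 24 months) that do not line up with the scan calendar

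*SAP*

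**What the plan says.** Protocol 9.7.2.1 announces the analysis: "A binary endpoint for PFS will also be analyzed at milestone time points". SAP 4.4.5.2.1 repeats it, names what is summarised, "The number and percentage of subjects who are progression free based on the above definition at 6, 9, 12, 18, and 24 months", and fixes the interval: "The two-sided 90% exact binomial confidence interval for the PFS at each time point will be calculated using the Clopper-Pearson method". The denominator is the FAS.

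The definition behind the count is a time-to-event one. A subject without progression or death "will be censored at the date when the last tumor assessment determines a lack of progression". SAP 4.3.3 says the same: "the subject will be censored at the last radiologic assessment showing no progression has occurred". SAP 4.3.3 also scores early withdrawals as non-responders, but only for ORR. There is no matching sentence for landmark PFS.

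Scans are scheduled at Week 10 and at Weeks 22, 28, 40, 52, 64, 76, 88 and 100 (Protocol 4.2.2.2). After that, "subjects will be followed by phone contact at quarterly intervals for survival status assessment" (Protocol 4.2.3), and SAP 4.3.1 states "As long-term FU visits only collect concomitant medication and vital status data, no windowing will be needed for this trial phase". Both documents single out the 6-month PFS rate to complement ORR when the trial is interpreted.

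**The concern.** A binomial proportion with exact limits needs a yes or no for every subject at every landmark. Censored time-to-event data do not supply one for a subject whose last clear scan comes before the landmark. Two things then decide the reported rate: an unwritten rule for those subjects, and where the landmark falls between scans. Progression is dated when a scan finds it, so a landmark just before a scan credits subjects with progression-free time that nobody has checked.

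At stake is the 6-month rate, the one PFS figure chosen to support the reading of ORR, and the 24-month rate, which concerns the subjects who did best.

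**Working it through.** **Inputs**
- Scan days: day = 1 + 7 × (week − 1). This reproduces the schedule: 64, 148, 190, 274, 358, 442, 526, 610, 694.
- Visit windows (SAP 4.3.1, Table 1): Week 22 = 144–152, Week 28 = 183–197, Week 40 = 267–281, Week 100 = 680–708. The protocol schedule is wider at some visits: ±1 week at Week 22 (141–155) and ±2 weeks at Week 40 (260–288).
- Month length: 30.4375 days, the SAP's conversion in 4.4.7.5. No month length is given for PFS.

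**Step 1: landmarks against scans**

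| Landmark | Day | Nearest scans |
|---|---|---|
| 6 months | 6 × 30.4375 = 182.6 | Week 22 (148), Week 28 (183–197) |
| 9 months | 273.9 | Week 40 (274) |
| 12 months | 365.25 | Week 52 (358) |
| 18 months | 547.9 | Week 76 (526), Week 88 (610) |
| 24 months | 730.5 | Week 100 (680–708), none later |

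- 24 months: 730.5 − 708 = 22.5 and 730.5 − 680 = 50.5 days. A completer scanned on schedule is censored that far short of the landmark.
- 6 months: an in-window Week 28 scan starts at Day 183, so progression first seen there is dated after the landmark. Deaths and unscheduled scans up to Day 182 still count.
- 9 months: progression found at Week 40 falls before or after the landmark depending on the day the scan was booked.

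**Step 2: size of the 6-month offset**

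The documents give no expected PFS for this combination. Assumption: a constant hazard matched to the 12-month PFS of 16.8% that Protocol 2.1 reports for second-line pembrolizumab.
- λ = −ln(0.168)/365.25 = 0.004884 per day.
- PFS at Day 148 = exp(−148λ) = 48.5%. PFS at Day 182.6 = exp(−182.6λ) = 41.0%. The difference is 7.5 points.
- This is an upper bound, because it treats every event as scan-detected, whereas deaths carry their own date.
- At 9 months, true PFS is 26.2%. If every Week 40 scan falls on or after the landmark, the rate shown is that of Day 190, exp(−190λ) = 39.5%.

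**Step 3: size of the missing scoring rule**

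A simulation of 400,000 subjects used the same hazard, scans on the planned days and all events scan-detected. The yearly dropout rates are assumed.

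| Landmark | Dropout per year | Censored = failure | Censored = progression-free | Kaplan-Meier |
|---|---|---|---|---|
| 6 months | 0% | 48.5% | 48.5% | 48.5% |
| 6 months | 10% | about 46% | about 50% | 48.6% |
| 6 months | 20% | about 43% | about 52% | 48.5% |
| 24 months | 0–20% | 0% | 3.4–15.2% | 3.3–3.4% |

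At 6 months the choice of rule moves the result by about 4 points (10% dropout) to 8.5 points (20% dropout). At 24 months Kaplan-Meier only carries the Week 100 value forward.

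**Step 4: does the replacement work?**

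Kaplan-Meier read at Day 197, the upper end of the Week 28 window, gives 39.5–39.6% at all three dropout rates. True PFS at Day 190 is 39.5%. Kaplan-Meier read at 6 calendar months instead stays at the Day 148 value (Step 3). Both parts of the change are therefore needed: the estimator and the scan-tied landmark.

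**The case against.** Three stronger readings are tempting, and the documents do not support them.

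- **That 24-month PFS can never be observed.** Progression or death before 24 months is observed. Protocol 4.2.5.1 continues imaging, on the schedule, for subjects who stop treatment without progression until progression is documented. Protocol 4.2.4 allows unscheduled visits. The gap concerns treatment completers without progression.
- **That censored subjects are counted as failures.** No sentence says so. A percentage of the FAS makes it the natural reading, but the only dropout-as-failure rule is for ORR. The 0% at 24 months in Step 3 depends on that reading.
- **That the 6-month rate simply is a Week 22 rate.** This holds for scan-detected progression in calendar months. The Protocol Synopsis loosely ties six months on trial to Days 148 and 190. SAP Table 1 also has analysis windows (Week 28 = Days 170–232, Week 40 = 233–316, Week 100 = after Day 652) under which each landmark would map to one visit. SAP 4.4.5.2.1 neither refers to that table nor treats landmark status as by-visit data, so this reading is available but not adopted. With 28-day months, 24 months would be Day 672, before the Week 100 scan, while 6 months (Day 168) would still rest on Week 22.

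It is also fair that the hazard comes from another drug in a second-line population, and that a constant hazard sits badly with the durable minority described in Protocol 2.8.2. Sampling error is larger than the offset: 14 of 33 (42%) has a 90% Clopper-Pearson interval of 28% to 58%. The two biases can partly cancel if censored subjects are scored as failures.

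These points limit the wording and the size. They do not supply the missing rule or assign a scan to any landmark.

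**Conclusion.** The point holds as a defect of method and specification in a secondary, descriptive endpoint. A crude FAS proportion is the wrong summary for a censored endpoint: either way of scoring censored subjects biases it, in opposite directions, and the plan does not choose one. The calendar adds an offset of at most about 7.5 points at 6 months, under the borrowed constant hazard and with all events scan-detected. It leaves 9-month status partly to booking dates, and completers without progression undocumented at 24 months by 22 to 50 days.

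The day arithmetic assumes calendar months and in-window scans. The percentages are illustrative. ORR, the Simon stopping rules and the type I error are not touched.

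**What to change.** In SAP 4.4.5.2.1 and Protocol 9.7.2.1:

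1. Replace the binary landmark analysis by Kaplan-Meier PFS rates with 90% confidence intervals. Name the interval method and report the number at risk.
2. Read the rates at the upper window limit of Weeks 28, 40, 52, 76 and 100, in place of 6, 9, 12, 18 and 24 months. State whether the SAP or the protocol windows apply, since they differ at Weeks 40 and 52.
3. Relabel 24-month PFS as Week 100 PFS unless imaging to Day 730 is shown to exist. Keep 24-month OS, which rests on survival contact and not on scans.
4. If a binary count is kept as well, state how a subject censored before the landmark is scored.
5. Carry the new labels into the endpoint lists in the Protocol Synopsis and SAP 2.6.2.

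The cost is wording only, because the Kaplan-Meier PFS curve is already planned. The drawback is that results are labelled by scan week, so comparison with published 6- or 12-month rates needs a footnote giving the day.
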